6.3.2 Follow-up of unresolved adverse events

Any AEs that are unresolved at the patient's last AE assessment in the study are followed up by the Investigator for as long as medically indicated, but without further recording in the electronic case report form (eCRF). AstraZeneca retains the right to request additional information for any patient with ongoing AE(s)/SAE(s) at the end of the study, if judged necessary.

6.3.3 Variables

The following variables will be collected for each AE:

- AE (verbatim)
- The date and time when the AE started and stopped
- Maximum intensity
- Whether the AE is serious or not
- Investigator causality rating against the IP (yes or no)
- Action taken with regard to IP
- Outcome.

In addition, the following variables will be collected for SAEs:

- Date AE met criteria for serious AE
- Date Investigator became aware of SAE
- AE is serious due to
- Date of hospitalisation
- Date of discharge
- Probable cause of death
- Date of death
- Autopsy performed
- Causality assessment in relation to study procedure(s)
- Causality assessment to other medication
- Description of AE.

It is important to distinguish between serious and severe AEs. Severity is a measure of intensity whereas seriousness is defined by the criteria in Section 6.2. An AE of severe intensity need not necessarily be considered serious. For example, nausea that persists for several hours may be considered severe nausea, but not a SAE unless it meets the criteria shown in Section 6.2. On the other hand, a stroke that results in only a limited degree of

disability may be considered a mild stroke but would be a SAE when it satisfies the criteria shown in Section 6.2.

The definitions for intensity rating are:

- Mild (awareness of sign or symptom, but easily tolerated)
- Moderate (discomfort sufficient to cause interference with normal activities)
- Severe (incapacitating, with inability to perform normal activities).

6.3.4 Causality collection

The Investigator will assess causal relationship between IP and each AE, and answer ‘yes’ or ‘no’ to the question ‘Do you consider that there is a reasonable possibility that the event may have been caused by the IP?’

For SAEs, causal relationship will also be assessed for other medication and study procedures. Note that for SAEs that could be associated with any study procedure the causal relationship is implied as ‘yes’.

A guide to the interpretation of the causality question is found in [Appendix A](#) to the Clinical Study Protocol.

6.3.5 Adverse events based on signs and symptoms

All AEs spontaneously reported by the patient or care provider or reported in response to the open question from the study site staff: ‘*Have you/the child had any health problems since the previous visit/you were last asked?*’, or revealed by observation will be collected and recorded in the eCRF. When collecting AEs, the recording of diagnoses is preferred (when possible) to recording a list of signs and symptoms. However, if a diagnosis is known and there are other signs or symptoms that are not generally part of the diagnosis, the diagnosis and each sign or symptom will be recorded separately.

6.3.6 Adverse events based on examinations and tests

The results from the Clinical Study Protocol-mandated laboratory tests and vital signs will be summarised in the CSR. Deterioration as compared with baseline in protocol-mandated laboratory values, vital signs should therefore only be reported as AEs if they fulfil any of the SAE criteria or are the reason for discontinuation of treatment with the IP.

If deterioration in a laboratory value/vital sign is associated with clinical signs and symptoms, the sign or symptom will be reported as an AE and the associated laboratory result/vital sign will be considered as additional information. Wherever possible the reporting Investigator uses the clinical, rather than the laboratory term (eg, anaemia versus low haemoglobin value). In the absence of clinical signs or symptoms, clinically relevant deteriorations in non-mandated parameters should be reported as AE(s).

Any new or aggravated clinically relevant abnormal medical finding at a physical examination as compared with the baseline assessment will be reported as an AE.

6.3.7 Liver biochemistry and evaluation of Hy's Law

Cases where a patient shows elevations in liver biochemistry may require further evaluation and occurrences of AST or ALT $\geq 3 \times$ ULN together with total bilirubin $\geq 2 \times$ ULN need to be reported as SAEs, except if the elevation is caused by the underlying sickle cell disease, ie, haemolysis, as judged by the Investigator. Please refer to [Appendix C](#) for further instruction on cases of increases in liver biochemistry and evaluation of Hy's Law.

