6.4 Reporting of serious adverse events

All SAEs have to be reported to the appropriate AstraZeneca representative, whether or not considered causally related to the IP, or to the study procedure(s). All SAEs will be recorded in the CRF.

If any SAE occurs in the course of the study, other than mentioned in Section 6.3.9, then Investigators or other site personnel inform the appropriate AstraZeneca representatives within 1 day, ie, immediately but **no later than 24 hours** of when he or she becomes aware of it (see also Section 6.4.1).

The designated AstraZeneca representative works with the Investigator to ensure that all the necessary information is provided to the AstraZeneca Patient safety data entry site **within 1 calendar day** of initial receipt for fatal and life-threatening events **and within 5 calendar days** of initial receipt for all other SAEs.

For fatal or life-threatening AEs where important or relevant information is missing, active follow-up is undertaken immediately. Investigators or other site personnel inform AstraZeneca representatives of any follow-up information on a previously reported SAE within 1 calendar day, ie, immediately but **no later than 24 hours** of when he or she becomes aware of it.

Once the Investigators or other site personnel indicate an AE is serious in the WBDC system, an automated email alert is sent to the designated AstraZeneca representative.

If the WBDC system is not available, then the Investigator or other study site staff reports a SAE to the appropriate AstraZeneca representative by telephone. The AstraZeneca representative will advise the Investigator/study site staff how to proceed.

The reference document for definition of expectedness/listedness is the IB for the AstraZeneca drug.

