- Complete the 3 Liver CRF Modules as information becomes available

If at any time (in consultation with the Study Physician) the PHL case meets serious criteria, report it as an SAE using standard reporting procedures.

Review and Assessment of Potential Hy's Law Cases

The instructions in this section should be followed for all cases where PHL criteria are met.

No later than 3 weeks after the biochemistry abnormality was initially detected, the Study Physician contacts the Investigator in order to review available data and agree on whether there is an alternative explanation for meeting PHL criteria other than DILI caused by the IMP. The AstraZeneca Global Clinical Lead or equivalent and Global Safety Physician will also be involved in this review together with other subject matter experts as appropriate.

According to the outcome of the review and assessment, the Investigator will follow the instructions below.

If there is an agreed alternative explanation for the ALT or AST and total bilirubin level elevations, a determination of whether the alternative explanation is an AE will be made and subsequently whether the AE meets the criteria for a SAE:

- If the alternative explanation is not an AE, record the alternative explanation on the appropriate CRF.
- If the alternative explanation is an AE/SAE, record the AE/SAE in the CRF accordingly and follow the AstraZeneca standard processes.

If it is agreed that there is **no** explanation that would explain the ALT or AST and total bilirubin level elevations other than the IMP:

- Report an SAE (report term 'Hy's Law') according to AstraZeneca Standard processes.

The 'Medically Important' serious criterion should be used if no other serious criteria apply.

As there is no alternative explanation for the HL case, a causality assessment of 'related' should be assigned.

If there is an unavoidable delay of over 3 weeks in obtaining the information necessary to assess whether or not the case meets the criteria for HL, then it is assumed that there is no alternative explanation until such time as an informed decision can be made.

- Report an SAE (report term ‘Potential Hy’s Law’) applying serious criteria and causality assessment as per above.

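### Protocol Section 6.3.7 and Appendix C give conflicting rules on when a combined transaminase and bilirubin elevation is an SAE, so SAE status and the reporting clock depend on which text a site follows

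*Protocol*

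**What the plan says.** **Protocol 6.3.7.** The combined elevation is AST or ALT at or above 3 × ULN together with total bilirubin at or above 2 × ULN. Such cases "need to be reported as SAEs, except if the elevation is caused by the underlying sickle cell disease", and that exception is glossed as "ie, haemolysis, as judged by the Investigator". No other exception is given, and neither a test of seriousness nor a review comes first. The section then refers to Appendix C "for further instruction on cases of increases in liver biochemistry and evaluation of Hy's Law".

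**Protocol 6.4.** For SAEs, sites "inform the appropriate AstraZeneca representatives within 1 day" of becoming aware. The endpoint events in Section 6.3.9 are carved out of this sentence; the liver cases in 6.3.7 are not.

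**Protocol Appendix C.** The same two thresholds define potential Hy's Law, with the added condition that the transaminase rise comes before, or on the same day as, the bilirubin rise. If at any time "the PHL case meets serious criteria, report it as an SAE using standard reporting procedures". Otherwise a joint review takes place: "No later than 3 weeks after the biochemistry abnormality was initially detected", the Study Physician contacts the investigator to agree whether there is another explanation. If there is one, "a determination of whether the alternative explanation is an AE will be made and subsequently whether the AE meets the criteria for a SAE". One branch ends with no event report: "If the alternative explanation is not an AE, record the alternative explanation on the appropriate CRF". If there is no other explanation, or if the necessary information is delayed beyond 3 weeks, an SAE is reported.

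**SAP 3.4.7.1 and 4.2.9.5.1.** These repeat the Appendix C definitions and plan laboratory-based summaries. They set no rule for SAE status.

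**The concern.** Section 6.3.7 classifies the case at detection with a single exception. Appendix C classifies it by seriousness or by the outcome of a review. A site that reads 6.3.7 and follows its pointer holds two instructions for one laboratory result, and neither text has a precedence clause.

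SAE status has consequences. It starts the 24-hour report and the onward transfer times in Section 6.4. It is one of the conditions for the sponsor's right to break the code for expedited reporting (Section 3.7). It also determines who is counted in the any-SAE row and who appears in the SAE listings (SAP 4.2.9.1). If sites follow different texts, identical results are reported and counted differently.

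**Working it through.** The point rests on no sample size, power or event-rate figure, so the check sets the two rules side by side and traces cases through them.

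**Routes to an SAE**

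- Section 6.3.7: the laboratory pair is enough, unless the investigator attributes it to sickle cell disease (haemolysis).
- Appendix C: (a) serious criteria met at any time; (b) review finds no explanation other than the study drug; (c) the agreed alternative explanation is itself an SAE; (d) information delayed beyond 3 weeks.

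**Cases**

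| Case | Section 6.3.7 with 6.4 | Appendix C |
|---|---|---|
| 1. Explained by a non-serious, non-sickle cause (the appendix's own examples are viral hepatitis, cholestasis and another drug) | SAE, 24 hours from awareness | Not an SAE: recorded as an AE, or as a CRF entry if the explanation is not an AE |
| 2. Unexplained, not otherwise judged serious | SAE, 24 hours from awareness | SAE only after the review, or once the 3-week limit is passed |
| 3. Attributed by the investigator to haemolysis | Exempt, on that judgement alone | No exemption: goes to joint review, and becomes an SAE if the information is overdue |

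**Counts.** Each patient whose only SAE would be a case 1 event adds one to the any-SAE row under 6.3.7 and none under Appendix C. Case 3 can differ in the opposite direction.

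**Timing (case 2).** Take detection and awareness on the same day, and an SAE report made on the last permitted review day. The gap between the two formal reports is then 21 − 1 = 20 days, or about 3 weeks. This is an outer limit, because 3 weeks is the latest time for the review and not its expected time.

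**Order of elevation.** A bilirubin rise that precedes the transaminase rise does not meet the Appendix C definition. Section 6.3.7 has no such condition, so the pair is within its scope.

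**Does the pointer to Appendix C settle it?** Suppose 6.3.7 governs and Appendix C only adds process. The appendix's instructions to report an SAE if serious criteria are met, after an unexplained review, or after 3 weeks would then be redundant for every case outside the haemolysis exception, because an SAE would already exist. Suppose instead that Appendix C governs. Then the unconditional rule and single exception in 6.3.7 are wrong. Neither reading leaves both texts intact.

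**The case against.** **A sequential reading.** Section 6.3.7 could set the reporting rule, with Appendix C covering investigation, causality and the final term. The appendix does provide for updating an SAE report after review. But that update applies to overdue cases, and the conditional SAE steps do not fit a case already reported. The objection supports a clarification; it does not remove the conflict.

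**Seriousness may close the gap.** Section 6.2 counts important medical events as serious, and Appendix A says they usually should be. If an investigator judges the laboratory pair medically important at once, both texts give an SAE. This stands, and it limits cases 1 and 2 to those not so judged. Appendix C itself assigns the medically important criterion by default only to unexplained or overdue cases.

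**The CRF-only branch.** In this population, a likely explanation that is not an AE is the underlying haemolysis, which 6.3.7 also exempts. There both texts can end with no SAE, so that branch alone is weak evidence.

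**Stronger inferences.** A reader might infer that the sponsor learns of a possible drug-induced liver injury up to 3 weeks late. The documents do not support this. Appendix C has the central laboratory alert the investigator and the sponsor's representative immediately, and requires the investigator to notify that representative of qualifying local results and of cases meeting the criteria. Only the formal SAE report can lag.

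A reader might also infer that the liver signal could be lost. SAP 4.2.9.5.1 tabulates, lists and plots these cases from laboratory values whatever their SAE status. Under Protocol 1.5.2 the DMC sees unblinded individual data and considers safety laboratory variables. Its stated trigger on fatal or life-threatening SAEs is unaffected, because such events are serious under both texts.

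**Conclusion.** The two texts conflict as written and must be reconciled. The conflict is confined to the three kinds of case in the table and to the order condition. It affects whether a formal SAE report is made, when it is due (a difference of up to about 3 weeks), and whether the any-SAE row and SAE listings are consistent across sites. No efficacy analysis is touched.

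The documents give no expected number of cases. The assumption here is that there will be few, but each is an important safety case. The conclusion also assumes that some cases would not be judged serious at detection; if all were, cases 1 and 2 would not differ. Which rule is right is for the sponsor to decide.

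**What to change.** 1. Reconcile Section 6.3.7 and Appendix C into one rule for when the combined elevation is an SAE, with one wording of the sickle cell exception, one statement of the order condition and one reporting clock, and state it identically in both places.
2. Before lock, compare the potential Hy's Law listing planned in SAP 4.2.9.5.1 with the SAE records, and confirm that every case was classed by that rule. The listing takes both elevations at any time after first dose, not necessarily together, so it is wide enough for the check whichever order condition is chosen.

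The cost is a protocol or safety-handling clarification and one reconciliation of an output already planned, with no extra patients or procedures. The SAP records that the sponsor ended the study early, so for this trial the pre-lock check carries most of the practical value.

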6.3.8 Assessment of bleeding events

Bleeding events will be recorded as AEs. The Investigator will do the classification of bleeding events. Bleeding events will be recorded in the eCRF.

For patients experiencing a bleeding event that fulfils criteria in more than 1 category, the bleed will be assigned to the most severe category. The bleeding definitions ([Mitchell et al 2011](#)) are:

- **Major bleeding:** defined as any fatal bleeding, clinically overt bleeding associated with a decrease in Hb of at least 20 g/L (2 g/dL), bleeding that is retroperitoneal, pulmonary, intracranial, or otherwise involves the central nervous system or bleeding that requires surgical intervention in an operating suite.
- **Clinically relevant non-major bleeding:** defined as overt bleeding for which a blood product is administered and which is not directly attributable to the patient's underlying medical condition, and bleeding that requires medical or surgical intervention to restore haemostasis, other than in an operating suite.
- **Minor bleeding:** defined as any overt or macroscopic evidence of bleeding that does not fulfil the above criteria for either major bleeding or clinically relevant, non-major bleeding. Menstrual bleeding resulting in a medical consultation and/or intervention will be classified as a minor bleeding event.

6.3.9 Vaso-occlusive crisis (VOCs) and acute SCD complications

A VOC and acute SCD complications (TIA/ischaemic stroke, hepatic sequestration and splenic sequestration, priapism and dactylitis) occurring during the study should be recorded by the Investigator as AEs. For a definition and collection of VOCs, see Section [5.1.1](#) and for acute SCD complication, see Section [5.1.5](#).

- A VOC fulfilling the criteria should also be recorded as an adverse event with the diagnosis Sickle cell anaemia with crisis.
- If the VOC event includes symptoms of other acute SCD complications, these should also be recorded, but separately from the VOC event in the eCRF.

6.3.10 Procedures in relation to COVID-19 infection

If a patient presents with clinical signs and symptoms consistent with COVID-19 infection, the Investigator should request a test where possible and this should be recorded in the AE field of the eCRF as follows:

- If test is positive, record as “COVID-19 confirmed”.
- If test is negative, record the AE/SAE signs and symptoms and/or other diagnosis.
- If test is not available and signs and symptoms, as judged by the Investigator, are highly suspicious of COVID-19 infection, record as “COVID-19 suspected”.

If other concurrent diagnoses exist, eg, pneumonia, the Investigator should record as separate AEs.

If an AE/SAE is associated with COVID-19, the Investigator should determine whether the patient’s IP should be continued, temporarily interrupted or permanently stopped. Refer to Section 3.9.4 for guidance on procedures in relation to COVID-19.

All AE reporting instructions in this section and SAE reporting in Section 6.4 also apply to any AE/SAE associated with COVID-19.

6.4 Reporting of serious adverse events

All SAEs have to be reported to the appropriate AstraZeneca representative, whether or not considered causally related to the IP, or to the study procedure(s). All SAEs will be recorded in the CRF.

If any SAE occurs in the course of the study, other than mentioned in Section 6.3.9, then Investigators or other site personnel inform the appropriate AstraZeneca representatives within 1 day, ie, immediately but **no later than 24 hours** of when he or she becomes aware of it (see also Section 6.4.1).

The designated AstraZeneca representative works with the Investigator to ensure that all the necessary information is provided to the AstraZeneca Patient safety data entry site **within 1 calendar day** of initial receipt for fatal and life-threatening events **and within 5 calendar days** of initial receipt for all other SAEs.

For fatal or life-threatening AEs where important or relevant information is missing, active follow-up is undertaken immediately. Investigators or other site personnel inform AstraZeneca representatives of any follow-up information on a previously reported SAE within 1 calendar day, ie, immediately but **no later than 24 hours** of when he or she becomes aware of it.

Once the Investigators or other site personnel indicate an AE is serious in the WBDC system, an automated email alert is sent to the designated AstraZeneca representative.

If the WBDC system is not available, then the Investigator or other study site staff reports a SAE to the appropriate AstraZeneca representative by telephone. The AstraZeneca representative will advise the Investigator/study site staff how to proceed.

The reference document for definition of expectedness/listedness is the IB for the AstraZeneca drug.

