1.5.2 Data Monitoring Committee

A DMC composed of independent SCD paediatric experts and including a platelet expert and statistician, will be appointed for this study and will report to the SC. The DMC will be responsible for safeguarding the interests of the patients in the study by assessing the safety of the intervention during the study, and for reviewing the overall conduct of the clinical study. The DMC will have access to unblinded individual data and be able to evaluate these while the study is ongoing. The DMC meeting schedule is shown in [Table 1](#). Additional meetings could be initiated by the DMC chair or the Sponsor as needed.

The DMC will consider recommending study termination for any episode of bleeding deemed related to the ticagrelor treatment that is fatal, or is a spontaneous intracranial haemorrhage, or if the accumulating data suggest a strong likelihood of excessive haemorrhagic events possibly related to ticagrelor that require medical intervention as reported by the Investigator. Study termination will also be considered if the number of fatal or life-threatening serious adverse events (SAEs), including but not limited to bleedings, is greater in ticagrelor-treated patients compared to placebo.

The DMC will make recommendations on the progression of the study based on the totality of data (eg, AEs, safety laboratory variables, ticagrelor exposure and platelet inhibition) or other findings putting patients at undue risk. The Sponsor has the final decision on study progression including amendments, etc.

Additionally, the DMC will do a formal interim PD assessment when 60 patients have had their PK/PD sampling after 4 weeks in the study. In this interim PD assessment, the mean of pre-dose and 2 hours post dose PRI values at 4 weeks will be calculated for each individual and compared to their respective baseline values. The population mean of the platelet inhibition in the ticagrelor arm is expected to be above 35% during the study. If there is a risk of not achieving the targeted inhibition level of 35% to 80% in the study, the first task of the DMC would be to investigate if the PK values and the PK/PD relationship are as expected and in line with earlier documented PK/PD data of ticagrelor. If any finding is deemed by the DMC to not be in accordance with expected PK and PD data and all other reasons for the unexpected findings are ruled out, they will contact the Sponsor and ask for proof of treatment

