6.4.1 Reporting of SAEs that are also endpoints in the study

Efficacy endpoints in the study (VOCs and acute SCD complications [TIA/ischaemic stroke, hepatic sequestration and splenic sequestration, priapism and dactylitis]) fulfilling the criteria for SAE will not be reported by AstraZeneca to health authorities to avoid unnecessary unblinding of efficacy endpoints that are also SAEs.

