6.7 Medication error

For the purposes of this clinical study a medication error is an unintended failure or mistake in the treatment process for an AstraZeneca study drug that either causes harm to the subject or has the potential to cause harm to the subject.

A medication error is not lack of efficacy of the drug, but rather a human or process related failure while the drug is in control of the study site staff or subject.

Medication error includes situations where an error:

- Occurred
- Was identified and intercepted before the patient received the drug
- Did not occur, but circumstances were recognised that could have led to an error.

Examples of events to be reported in clinical studies as medication errors:

- Drug name confusion
- Dispensing error, eg, medication prepared incorrectly, even if it was not actually given to the patient

- Drug not administered as indicated, for example, wrong route or wrong site of administration
- Drug not taken as indicated, eg, tablet dissolved in water when it should be taken as a solid tablet
- Drug not stored as instructed, eg, kept in the fridge when it should be at room temperature
- Wrong patient received the medication (excluding IXRS errors)
- Wrong drug administered to patient (excluding IXRS errors).

Examples of events that **do not** require reporting as medication errors in clinical studies:

- Errors related to or resulting from IXRS - including those which lead to 1 of the above listed events that would otherwise have been a medication error
- Patient accidentally missed drug dose(s), eg, forgot to take medication
- Accidental overdose (will be captured as an overdose)
- Patient failed to return unused medication or empty packaging
- Errors related to background and rescue medication, or standard of care medication in open-label studies, even if an AstraZeneca product.

Medication errors are not regarded as AEs but AEs may occur as a consequence of the medication error.

If a medication error occurs in the course of the study, then the Investigator or other site personnel informs the appropriate AstraZeneca representatives within 1 day, ie, immediately but **no later than 24 hours** of when he or she becomes aware of it.

The designated AstraZeneca representative works with the Investigator to ensure that all relevant information is completed within 1 or 5 calendar days if there is an SAE associated with the medication error (see Section 6.4) and within 30 days for all other medication errors.

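### The 24-hour site-to-sponsor deadline in Section 6.4 excepts every VOC and acute SCD complication, fatal or life-threatening ones included, so such events could reach a DMC review late

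*Protocol*

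**What the plan says.** Protocol Section 6.4 opens with a general duty: "All SAEs have to be reported to the appropriate AstraZeneca representative, whether or not considered causally related to the IP". That sentence carries no time limit. The time limit comes in the next paragraph, where the 24-hour rule for a first report begins "If any SAE occurs in the course of the study, other than mentioned in Section 6.3.9".

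Section 6.3.9 describes the excepted class as "A VOC and acute SCD complications (TIA/ischaemic stroke, hepatic sequestration and splenic sequestration, priapism and dactylitis) occurring during the study". By the endpoint definition in Section 5.1.1, a VOC includes ACS. Section 6.3.9 does not qualify the class by seriousness, outcome or relatedness.

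Section 6.4.1, to which the 24-hour sentence also refers, says that endpoint events meeting SAE criteria "will not be reported by AstraZeneca to health authorities to avoid unnecessary unblinding".

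Section 1.5.2 sets the DMC's criteria. Besides the bleeding criteria, it states: "Study termination will also be considered if the number of fatal or life-threatening serious adverse events (SAEs", and continues that this applies when the number is greater on ticagrelor than on placebo. Bleedings are named there as an example and not as the limit, and endpoint events are not excluded.

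**The concern.** The exception makes sense for the ordinary hospitalised crisis, which is both expected and the trial's endpoint. As worded, though, it also takes a fatal ACS or a life-threatening stroke out of the only deadline that applies to a site's first report. The stated reason, avoidance of unblinding, belongs to onward reporting to authorities. A site that tells a blinded sponsor that an event has happened reveals no allocation, so that reason does not support dropping the site's deadline.

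The DMC's view of mortality and life-threatening events is at stake. Section 6.4.1 already keeps these events from health authorities, which puts more weight on DMC review as the check on them. Section 1.3 describes ACS as a common cause of death in SCD. If fatal or life-threatening endpoint events come in without a deadline, a scheduled DMC review could look at an incomplete comparison of the arms.

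**Working it through.** No arithmetic applies. The check is whether any other rule closes the gap that the exception opens. Each timed rule that could bear on a serious VOC or acute SCD complication was read for when its clock starts and whom it binds.

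1. **General duty (Section 6.4, first sentence).** It covers all SAEs and requires CRF recording. It gives no time limit.
2. **24-hour rule for first reports (Section 6.4).** This is the only site-to-sponsor clock for a new SAE. Section 6.3.9 events are excepted from it without qualification.
3. **1-day and 5-day rules (Section 6.4).** The shorter clock is counted from the time "of initial receipt for fatal and life-threatening events". Both start when the sponsor's representative has the report and govern its passage to the safety data entry site. Neither binds the site's first notification.
4. **Second 24-hour statement (Section 6.4).** It concerns follow-up information on an SAE that has already been reported.
5. **Automated e-mail alert (Section 6.4).** It fires once the site marks the event as serious in the data capture system. No time is set for doing that.
6. **Section 6.4.1.** It governs sponsor-to-authority reporting only.
7. **72-hour call (Sections 5.1.1.1 and 5.1.1.2).** This is contact between the investigator and the caregiver. It supports data collection but is not a report to the sponsor.
8. **Timeliness of recorded data (Section 5).** The protocol refers to the Clinical Study Agreement and gives no figure.
9. **SAP Sections 3.2.1, 3.4.1, 3.4.3 and 5.** They cover recording of VOCs, the AE collection period, recording of deaths as SAEs and the DMC's role. None adds a reporting deadline.

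So neither document gives a site a deadline for first notifying the sponsor of a serious VOC or acute SCD complication, whatever its outcome. Elsewhere the protocol does set such clocks. For a medication error, "then the Investigator or other site personnel informs the appropriate AstraZeneca representatives within 1 day", and overdoses (Section 6.5) and pregnancies (Section 6.6.1) are treated likewise. Those rules serve other purposes and prove no harm here. They show only that the protocol sets a one-day clock for other report types.

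Next, which DMC criteria are touched? Haemorrhagic stroke, intracranial haemorrhage and other bleeding are not in the Section 6.3.9 list, so bleeding SAEs stay under the 24-hour rule and the bleeding criteria are intact. Only the comparison of fatal or life-threatening SAEs is affected, and only through the Section 6.3.9 events that are fatal or life-threatening.

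**The case against.** The strongest reply is that only a deadline is missing. All SAEs must still be reported and recorded, and Section 5.1.1.1 lists the AE/SAE form among the data required for each VOC. Marking an event as serious alerts the sponsor automatically, and Section 9.4 says that entries are saved at once to the central database. An eDevice entry should lead to a call within 72 hours of onset, and telephone visits between site visits ask about AEs and SAEs. The remaining gap is therefore the time from site awareness to data entry. All of this stands, and it limits the consequence to possible delay.

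The reply is also right about the DMC. Its criterion is a matter for consideration, with recommendations resting on the totality of data. Table 1 schedules six evaluations, with further meetings as needed, so an event missed at one review can appear at the next. Sites are blinded, so there is no evident reason for delay to differ between arms.

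A deadline may exist in the Clinical Study Agreement, and the DMC charter may say how such events are handled. Neither was available, so the finding covers the protocol and SAP only. Under Section 9.2.2 the protocol prevails over the agreement on study conduct where the two are inconsistent, so an express exception is better settled in the protocol itself.

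None of this gives a reason for excepting fatal or life-threatening cases from the site's deadline.

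**Conclusion.** The point holds in a limited form. The exception in Section 6.4 is broader than the reason given in Section 6.4.1, and it leaves fatal or life-threatening VOCs and acute SCD complications without a stated site-to-sponsor deadline although they count towards a DMC criterion. The effect is possible late arrival at a DMC review. Its size cannot be given, because the documents state neither a rate of such events nor a typical reporting lag.

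A reader might infer more than the documents support:

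- **That serious crises need not be reported, or that data are lost.** The duty to report and record remains.
- **That every ischaemic stroke bears on the DMC's count.** Only a fatal or life-threatening one does.
- **That the number of VOCs expected from the sample size assumptions measures the problem.** That number would include crises treated at home and says nothing about fatal or life-threatening ones.
- **That reports would be long delayed, or that a single late report would reverse the DMC's conclusion.** No passage gives such a lag, and the criterion is a judgement, not an automatic trigger.

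The conclusion assumes that the documents not seen do not already set a deadline for these events. SAP Section 3.1.4.1 records that the sponsor ended the study early; the point concerns the rule as the protocol states it.

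**What to change.** In Section 6.4, limit the exception to Section 6.3.9 events that are neither fatal nor life-threatening. Fatal or life-threatening VOCs and acute SCD complications then follow the same 24-hour site-to-sponsor rule as other SAEs. Leave Section 6.4.1 unchanged, so that authority reporting and blinding stay as they are.

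The cost is one reworded sentence and a few more 24-hour reports from sites. Hospitalised crises that are not life-threatening stay exempt, and the analysis does not change.
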